7.1 Primary Endpoints

7.1.1 Safety and tolerability

- *Incidence of SAEs in rhu-pGSN vs placebo groups*

7.1.2 Efficacy

- *Proportion of subjects alive not on vasopressors, mechanical ventilator, and dialysis on Day 14.*

7.2 Secondary Endpoints

7.2.1 Safety and tolerability

- *Incidence, causality, and severity of AEs (graded according to the National Cancer Institute [NCI] Common Terminology Criteria for Adverse Events [CTCAE] version 5.0) in rhu-pGSN vs placebo groups*
- *Frequencies of new or worsening clinically significant laboratory abnormalities in rhu-pGSN vs placebo groups*
- *Mortality rate irrespective of cause at Days 28 and 90*

7.2.2 Efficacy

- *Daily change in 9-point WHO severity score through at least Day 14*
- *All-cause mortality at Days 28 and 90; time to death (Kaplan-Meier survival analysis)*
- *Proportion of subjects alive on Days 7, 14, 28, 60, and 90 without:*
 - *Ongoing use of vasopressors*
 - *Ongoing intubation/mechanical ventilation*
 - *Ongoing residence in an ICU*
 - *New ongoing need for dialysis/renal replacement therapy (RRT)*
- *Proportion of subjects discharged to home or immediate prior residence by Day 28*
- *Days on the ventilator*
- *Length of stay (LOS) in hospital and in ICU (days)*
- *Re-admission to an acute-care hospital up to Day 90*

7.2.3 PK (Optional)

- *PK for rhu-pGSN including maximum concentration (Cmax), time to maximum concentration (Tmax), terminal half-life (T1/2), area under the curve from time zero to 8 hours (AUC0-8), area under the curve from time 0 to infinity (AUCinf) for Dose #1 within 15 minutes predose, and at 1 (± 15 min), 2 (± 15 min), 6 (± 30 min), and 12 (± 30 min) hours after end of administration (but prior to Dose #2); for Dose #3 within 15 minutes predose, and at 1 (± 15 min), 2 (± 15 min), 6 (± 30 min), 12 (± 30 min) and 24 (± 30 min) hours after the end of administration (participants refusing these blood samplings can enter and remain in the trial).*

7.2.4 Immunogenicity

- *Presence of anti-pGSN antibodies on Days 1 (predose), 28, and 90*

7.3 Exploratory Endpoints

7.3.1 Biomarkers

- *Changes in biomarkers and radiologic imaging over time with treatment*
- *Relationship of baseline biomarkers to clinical outcomes*

8 Statistical Methods

8.1 General Conventions

All analyses will be done using SAS (version 9.4, SAS Institute Inc., Cary, NC, USA).

Efficacy and Safety endpoints will be analyzed in a descriptive manner. Continuous data will be reported using the following descriptive statistics:

1. Number of observations (n)
2. Mean and Standard deviation (SD)
3. Interquartile Range (IQR)
4. Minimum (min) and Maximum (max)
5. Median

In addition:

6. Geometric mean & Standard deviation
7. Coefficient of variation (CV%)
8. Geometric CV%

will be reported for plasma concentration data and PK parameters. Categorical data will be presented using frequency (n = number of subjects; m = number of events) and percentage (%).

Listings will be provided for all data recorded in eCRF to study subject profiles. All listings will be sorted by treatment, subject ID, and date (if applicable). Unscheduled visit data will only be listed and not included in summaries.

All p-values will be displayed to four decimal places, with p-values less than 0.0001 presented as '<0.0001' and p-values greater than 0.9999 presented as '>0.9999'. Minimum and maximum values will be reported in the units of collection with 3 decimals being maximum value; the mean will be presented with 1 decimal place more and the standard deviation 2 decimal places more than the units of collection. Percentages for categorical summaries will be represented to 1 decimal place.

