## **5. TRIAL OBJECTIVES AND ENDPOINTS**

### **5.1. Objectives**

#### **5.1.1. Primary Objective**

- To assess the efficacy (survival without organ failure on Day 14) of IV rhu-pGSN plus SOC vs placebo plus SOC (hereafter referred to as rhu-pGSN vs placebo) administered to hospitalized subjects with a primary diagnosis of COVID-19 pneumonia and in Part 1, a severity score of 4, 5, or 6, or for Part 2, intubated without ECMO with a severity score of 6 or 7 on the World Health Organization (WHO) 9-point severity scale
- To evaluate the safety (incidence of SAEs) of IV rhu-pGSN administered to hospitalized subjects with a primary diagnosis of COVID-19 pneumonia and in Part 1, a severity score of 4, 5, or 6, or for Part 2, intubated without ECMO with a severity score of 6 or 7 on the WHO 9-point severity scale

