## 7. STUDY POPULATION

### 7.1. Number of Subjects

Part 1: A total of 60 evaluable participants randomized 1:1 to rhu-pGSN:placebo (30:30 subjects).

Part 2: A total of 20 evaluable participants randomized 1:1 to rhu-pGSN:placebo (10:10 subjects).

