## **11.4. Criteria for Evaluation and Statistical Methods**

### **11.4.1. Safety**

AE data will be summarized by counts and proportions of subjects having an AE, each AE type, and an AE of each System Organ Class. These summaries will be provided for the rhu-pGSN and placebo groups separately. SAEs will be summarized similarly. Reasons for any early discontinuations will be summarized similarly.

Laboratory data in relation to normal range values will be summarized via counts and percentages of subjects below, within, and above the respective normal range, and by summary statistics (N, mean, median, standard deviation, minimum, maximum, 90% confidence intervals, etc.) for baseline, each observed time point, and change from baseline at each observed time point for continuous lab endpoints.

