12.10.1.1 Overall Adverse Events

Number and percentage of subjects and number of events will be summarized by treatment for the following categories:

1. All adverse events reported
2. Treatment emergent adverse events (TEAEs)
3. Serious TEAEs
4. Related TEAEs
5. Related Serious TEAEs
6. Adverse events led to death
7. Adverse events led to study discontinuation
8. Grade 3 or higher TEAEs
9. Grade 3 or higher related AEs
10. Adverse events by severity
11. Injection related Adverse Events by Severity
12. Adverse events by relationship to IMP
13. Adverse events by relationship to study procedure
14. Adverse events by outcome
15. Adverse events by action taken with treatment

Severity grading is based on NCI CTCAE, version 5.0. Percentages will be based on Safety analysis set. If a subject has multiple occurrences with different intensity/ relationships, then all the occurrences will be counted.

In DDP: Table 14.3.1.1

All adverse events will be listed by subject and system organ class. Adverse events will be grouped by subjects. Day the Adverse event started, and Duration of AEs will also be included in the listing.

In DDP: Listing 16.2.7.1

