12.10.1.2 Summary of Treatment Emergent Adverse Events by SOC and PT

Number and percentage of subjects and number of adverse events will be summarized by treatment, system organ class and preferred terms. Percentages will be based on safety analysis set. Events will be displayed in the descending order of frequency in “Total”.

The same will be repeated for treatment-emergent related AEs, treatment-emergent serious AEs, treatment-emergent related serious AEs. Serious AEs and Deaths will be listed separately for respective sections in CSR (as per ICH E3).

In DDP: Tables 14.3.1.2 to 14.3.1.8, Tables 14.3.2.1 and 14.3.2.2

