16.1 Summary of Statistical Analyses

Endpoints	Analysis Set	Primary Analyses	Supportive Analyses
Incidence of SAEs in rhu-pGSN vs placebo groups	Safety analysis set	Descriptive Summaries	-
Proportion of subjects alive not on vasopressors, mechanical ventilator, and dialysis on Day 14.	FAS (primary), Per-Protocol analysis set	Cochran-Mantel-Haenszel (CMH) method	-
Adverse Events, Clinically Significant Laboratory Results	Safety analysis set	Descriptive Summaries	-
Change in WHO Severity Score	FAS, Per-Protocol analysis set	Shift summaries, Box Plots, MMRM	-
Mortality Rate and Time to Death	FAS (primary), Per-Protocol analysis set	Log Rank Test, Cox Regression Model, Kaplan-Meier Curve	-
Proportion of Subjects alive without support	FAS (primary), Per-Protocol analysis set	CMH	-
Days on the Ventilator	FAS (primary), Per-Protocol analysis set	Descriptive Summaries, Wilcoxon Rank Sum Test	-
Hospitalization and ICU days	FAS (primary), Per-Protocol analysis set	Descriptive Summaries	-
Plasma Concentration	PK analysis set	Descriptive Summaries and Plots	
PK Parameters	PK analysis set	Descriptive Summaries	-
Immunogenicity	PK analysis set	Descriptive Summaries	-
Biomarkers	Safety analysis set	Descriptive Summaries	-

17 Change Log

Version	Authored by	Change Date	Change Details	Reviewed by	Review Date
1.00	[name] [name]	05-Aug-2021	First version approved	[name]	05-Aug-2021

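### SAE incidence is a primary endpoint worded as rhu-pGSN versus placebo, but the plan tabulates it by arm with no between-arm difference or interval, so similar percentages could not show similar safety.

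*SAP*

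**What the plan says.** Both documents list SAE incidence as a primary endpoint in the same words: "Incidence of SAEs in rhu-pGSN vs placebo groups" (Protocol 5.2.1, SAP 7.1.1, and again in the SAP 16.1 table). The matching primary objective in Protocol 5.1.1 is "To evaluate the safety (incidence of SAEs) of IV rhu-pGSN administered to hospitalized subjects".

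The analysis is described in these places:

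- Protocol 11.4.1, after specifying counts and proportions of subjects with AEs: "These summaries will be provided for the rhu-pGSN and placebo groups separately. SAEs will be summarized similarly".
- SAP 8.1, as a general convention: "Efficacy and Safety endpoints will be analyzed in a descriptive manner", and "Categorical data will be presented using frequency (n = number of subjects; m = number of events) and percentage".
- SAP 12.10.1.1, whose category list includes serious TEAEs: "Number and percentage of subjects and number of events will be summarized by treatment for the following categories".
- SAP 12.10.1.2, for the table by system organ class and preferred term: "The same will be repeated for treatment-emergent related AEs, treatment-emergent serious AEs, treatment-emergent related serious AEs".
- SAP 16.1, which assigns the endpoint descriptive summaries on the Safety Analysis Set and leaves the supportive-analysis column blank.

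The operative rules are SAP 12.10.1.1, 12.10.1.2 and 16.1. The SAP 8.1 sentence is general. It also covers efficacy, which the SAP then analyses inferentially.

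**The concern.** The endpoint names two groups and sets one against the other, but the planned output holds two separate percentages and nothing that measures the gap between them. Elsewhere the SAP does measure the gap:

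- Primary efficacy gets a common risk difference with an 80% CI (12.9.1.1).
- WHO score change gets differences with 95% CIs and p-values (12.9.2.1.3).
- Discharge gets a risk difference with a 95% CI and a Fisher p-value (12.9.2.4).
- Days in hospital, in ICU and on the ventilator get a difference, a 95% CI and a p-value (12.9.2.6).

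Of the two primary endpoints, only the safety one has no between-arm estimate.

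What is at stake is how the result will be read. With 30 subjects per arm, two similar percentages are compatible with a sizeable true excess, and a table without an interval does not show that. The matter is not idle here. Protocol 4.7.1 calls the safety database limited (24 rhu-pGSN recipients). In the earlier ICU study in Protocol 4.4.2, 7 of 21 treated and 0 of 7 placebo patients died, which the protocol attributes most probably to baseline imbalance.

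**Working it through.** **The plan's own figure.** The documents give no rate, precision or tolerable excess for SAEs. Their only sizing is for efficacy (Protocol 11.2, SAP 4.2): N=54, about 80% power, one-sided alpha 0.2, 20% versus 5%, minimum significant difference 8.4 points. With z = 0.8416 for both error rates and a mean proportion of 0.125:

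n per arm = [0.8416·√(2·0.125·0.875) + 0.8416·√(0.20·0.80 + 0.05·0.95)]² / 0.15² = [0.8416·(0.4677 + 0.4555)]² / 0.0225 = 26.8, so 27 per arm, or 54.

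Power at 27 per arm is 80.1%, and the smallest significant contrast with 20% is 11.6%, a gap of 8.4 points. The efficacy sizing reproduces, but it says nothing about SAEs.

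**Inputs for SAEs.** Part 1 has 30 evaluable subjects per arm (Protocol 7.1). The SAE rate is assumed, over 10% to 50%.

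**Formula.** The Wilson limits for each arm are

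l, u = [p + z²/2n ± z·√(p(1−p)/n + z²/4n²)] / (1 + z²/n).

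The Newcombe interval for d = p₁ − p₂ (rhu-pGSN minus placebo) runs

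from d − √[(p₁−l₁)² + (u₂−p₂)²] to d + √[(u₁−p₁)² + (p₂−l₂)²].

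**Worked case, 6/30 in each arm, 95%.** z² = 3.8415 and 1 + z²/n = 1.128. The Wilson limits are 0.095 and 0.373. The upper limit is 0 + √(0.173² + 0.105²) = 0.202, or 20.2 points.

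**Equal counts, 30 per arm:**

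| SAE subjects in each arm | Rate | 95% Newcombe | 80% Newcombe |
|---|---|---|---|
| 3 | 10% | ±16.9 | ±10.5 |
| 4 | 13% | ±18.2 | ±11.6 |
| 6 | 20% | ±20.2 | ±13.3 |
| 9 | 30% | ±22.3 | ±14.9 |
| 12 | 40% | ±23.5 | ±15.8 |
| 15 | 50% | ±23.8 | ±16.1 |

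The simple Wald formula locates the 20-point threshold in the same place: 1.96·√(2p(1−p)/30) ≥ 0.20 requires p(1−p) ≥ 0.156, so p of about 19.4% or more (up to 80.6%).

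**Unequal counts, 95% Newcombe.** One extra SAE subject on rhu-pGSN gives upper limits of 20.9 points (4 versus 3), 23.0 (6 versus 5) and 25.6 (10 versus 9). At 9 versus 6 the interval is −11.8 to +30.7.

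**Part 2, 10 per arm.** Equal counts of 1 to 5 give ±31.5 to ±37.3 points.

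**The case against.** The strongest reply is that descriptive safety reporting is the stated and consistent plan. Protocol 11.1 and 11.4.1 specify counts and proportions, and the SAP follows them. SAP 8.2 recognises one primary hypothesis, for efficacy, and no safety hypothesis or margin exists. The safety objective names no comparator, whereas the efficacy objective beside it does. The same versus-placebo label is attached to AEs and laboratory abnormalities, which are also only tabulated. The gravest harm is compared: time to death gets a log-rank test, Kaplan-Meier estimates with 95% CIs and a hazard ratio with 95% CI (SAP 12.9.2.2.1 and 12.9.2.2.2), and death or organ support at Day 14 gets a risk difference. The DSMB also reviews reported deaths and treatment-emergent SAEs during the trial (Protocol 6.2). Finally, a reader can compute the interval from the counts.

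Much of this stands. The plan is not internally inconsistent on this point, and a reader who inferred that harm goes uncompared altogether would be wrong. A reader might also infer that the sponsor intends to claim similar safety; no passage plans such a claim.

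What does not stand is that these points make the estimate unnecessary. Mortality analyses do not report SAE incidence. DSMB review protects subjects during conduct and does not report the endpoint. An interval is an estimate, so it needs no hypothesis and raises no multiplicity question. If it is left to readers, the method, confidence level and event window are chosen after unblinding, for a primary endpoint.

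**Conclusion.** The point holds as an avoidable gap in the analysis of a primary endpoint. It is not an error in the plan's figures. The gap itself does not depend on any assumed rate: no section gives a between-arm estimate or interval for SAE incidence.

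Its size does depend on assumptions. With 30 per arm, 95% confidence and identical counts, an excess of up to about 17 to 24 points on rhu-pGSN remains open for SAE rates of 10% to 50%.

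A reader might go further and say flatly that the trial cannot exclude a 20-point excess. The documents do not support that without conditions. With equal counts it needs a 95% interval and an SAE rate of about 20% or more. At 3/30 in each arm the upper limit is 16.9 points, and at the 80% level used for primary efficacy, 6/30 in each arm gives 13.3. A rate of 20% or more is plausible in severe COVID-19 pneumonia with SAEs followed to about Day 90. The nearest anchor is the 20% placebo figure in the sizing, which reads as the Day 14 failure rate, but that is not an SAE rate.

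**What to change.** In SAP 12.10.1 and in the SAE row of SAP 16.1, add for the Safety Analysis Set:

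- the number and proportion of subjects with at least one treatment-emergent SAE, by arm, over the protocol's SAE collection period;
- the risk difference, rhu-pGSN minus placebo, with a Newcombe or score 95% CI.

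Report it by study part, since Protocol 11.1 has the two parts analysed separately. The SAP as written describes only the score 4 to 6 population, so the Part 2 row belongs wherever the Part 2 outputs are specified.

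Align the collection window first. Protocol Table 5, footnote q, records SAEs from consent through study completion (the Day 90 visit). Protocol 10.1.2 starts after consent and randomization and ends 90 days after the last dose.

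No p-value is needed. Power against a true 20-point excess at two-sided 0.05 is only 34% to 49% for placebo rates from 40% down to 10%, so a non-significant test would invite the very misreading at issue.

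The cost is one extra table row and an interval that will look wide, especially in Part 2. No extra data or subjects are required.

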8.2 Multiplicity Adjustment

Since there is only one primary efficacy hypothesis defined in the study as per the protocol (difference between treatments in the proportion of surviving patients off vasopressors, the ventilator, and dialysis on Day 14), multiplicity adjustment is not required for the primary endpoint. Hypothesis tests for secondary endpoints will be performed, and caution must be taken when interpreting these results. Adjusted p-values using Bonferroni method may be reported from post-hoc tests if deemed necessary.

8.3 Re-estimation of Sample Size

Exploratory analyses to compare the efficacy endpoint data from the rhu-pGSN group from this study to that of external control data may be carried out if appropriate. Sample size may be increased to improve the precision of the estimates of between-treatment comparisons if appropriate and if drug supplies are available.

9 Data handling Procedures

9.1 Handling Missing/Incomplete Data

Plasma concentration results missing, or below lower limit of quantification (LLOQ) will be set to 0 for pre-dose measurements. Missing PK parameters will be imputed at the LLOQ value. Plasma concentration results missing or below LLOQ for post-dose measurements will not be imputed.

Handling of missing data for efficacy analyses is defined in the respective sections below.

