#### **4.3. Plasma Gelsolin**

Plasma gelsolin (pGSN) is a human protein produced and secreted by virtually every cell type, and it circulates at high levels in the blood of healthy individuals. At normal levels of 200-300 mg/L, it is the fourth most abundant protein in the circulation.

The therapeutic protein developed by BioAegis is rhu-pGSN and was formerly referred to as BG9385. It is identical to the complete natural protein and is comprised of 755 amino acids. The protein, like the natural protein, is non-glycosylated. The protein consists of six repeated domains, which make up three distinct actin binding sites, two that bind globular actin (G-actin) and one that binds filamentous actin (F-actin). Domain 1 plus the first 10 amino acids of domain 2 of gelsolin is the minimal fragment size required for its actin severing activity. Rhu-pGSN contains multiple calcium binding sites that regulate its activity. It is a highly conserved protein, as far back as drosophila.

Plasma gelsolin modulates inflammation while at the same time, boosting the body's ability to clear pathogens. It functions through mechanisms quite distinct from anti-inflammatory agents, which are antagonists of specific mediators or inhibitors of specific enzymes. Plasma gelsolin functions through a pleiotropic mechanism of action, scavenging toxic actin, binding inflammatory mediators and enhancing pathogen clearance. pGSN levels decrease markedly in a variety of clinical conditions such as acute respiratory distress syndrome, sepsis, major trauma, prolonged hyperoxia, malaria, and liver injury. The strength of the correlation between magnitude of decline in pGSN and likelihood of mortality is especially striking (Lee et al, 2006; 2008; 2009; Osborn et al, 2008). Specifically, a study of adult patients hospitalized with CAP showed that lower pGSN concentrations were significantly associated with more severe clinical outcomes (Self et al, 2018). Repletion of depressed plasma gelsolin levels with rhu-pGSN is expected to benefit patients through four distinct mechanisms that have been described in the literature:

1. Sequestration of released actin from sites of damage. This sequestration causes local depletion of pGSN while leaving large stores of pGSN continuing to circulate in healthy individuals. Modest reduction of systemic pGSN levels is then restored after healing is complete (Haddad et al, 1990; Lee et al, 1992).

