### **9.3.      Pharmacokinetic Assessments**

Blood for PK will be drawn at the following time points:

- For Dose #1: within 15 minutes predose, and at 1 ( $\pm 15$  min), 2 ( $\pm 15$  min), 6 ( $\pm 30$  min), and 12 ( $\pm 30$  min) hours after the end of dose administration (but prior to Dose #2)
- For Dose #3: within 15 minutes predose, and at 1 ( $\pm 15$  min), 2 ( $\pm 15$  min), 6 ( $\pm 30$  min), 12 ( $\pm 30$  min) and 24 ( $\pm 30$  min) hours after the end of dose administration

Samples should be spun and plasma frozen and sent to a central lab for analysis. Plasma samples will be analyzed for maximum concentration ( $C_{max}$ ), time to maximum concentration ( $T_{max}$ ), terminal half-life ( $T_{1/2}$ ), area under the curve from time zero to 8 hours ( $AUC_{0-8}$ ), area under the curve from time 0 to infinity ( $AUC_{inf}$ ).

Participants who refuse some or all PK blood samplings can remain in the trial. However, PK sampling is to be highly encouraged.

For Dose #3, the last PK sample will occur on Day 3 (i.e., 24 hours after the end of third study drug administration which was initiated 36 hours after the first dose).

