10.7 PK Analysis Set

The PK Analysis Set will include all subjects in the FAS who have sufficient concentration data to obtain reliable estimates of the key PK parameters and have no important protocol deviations that can influence the validity of the data for the PK endpoints.

PK Analysis Set will be finalized after review of concentration data post DBL and unblinding.

11 Analysis Variables

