11.7 Baseline

All analysis datasets having measurements taken at more than one visit/time point will have baseline flags. Baseline is defined as the latest non-missing measurement prior to IMP administration including repeat assessments and unscheduled visits. In case of multiple results at the same date/time, worst result will be considered as baseline in the following order or hierarchy: Abnormal CS, Abnormal NCS, Normal, Missing.

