12.9.5 Plasma Concentration

12.9.5.1 Continuous Summary

Descriptive summaries including geometric mean and SD, co-efficient of variation (%), geometric co-efficient of variation (%) of plasma concentrations will be presented by gender, time point and treatment groups. The summary will be based on PK analysis set.

All plasma concentration results will be listed by subject for PK analysis set.

In DDP: Table 14.5.1.1, Listing 16.2.10.2

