12.9.5.2 Plasma Concentration Time Plots

Drug concentration profiles will be generated as follows:

- Mean Plasma concentration vs time will be presented for subjects within each treatment group along with error bars. Each group will be differentiated by color and symbol with appropriate legend. Y axis will be plasma concentration in ng/mL and X axis will be timepoints in hours. X axis will be displayed linearly proportionate to the actual timepoints.
- Log transformed plots will also be presented for the mean plots.

In DDP: Figures 14.5.1.2 and 14.5.1.3

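### SAP 9.1 turns a missing pre-dose level of an endogenous protein into 0 and a missing PK parameter into the assay limit; both should stay missing

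*SAP*

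**What the plan says.** SAP 9.1 has three rules for PK data.

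- Pre-dose concentrations: "Plasma concentration results missing, or below lower limit of quantification (LLOQ) will be set to 0 for pre-dose measurements".
- PK parameters: "Missing PK parameters will be imputed at the LLOQ value".
- Post-dose concentrations that are missing or below the LLOQ are not imputed.

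These rules feed the following sections.

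- SAP 12.9.5.1 requires descriptive statistics that include the geometric mean and the "geometric co-efficient of variation (%) of plasma concentrations will be presented by gender, time point and treatment groups".
- SAP 12.9.5.2 plots mean concentrations, also on a log scale: "Y axis will be plasma concentration in ng/mL and X axis will be timepoints in hours".
- SAP 12.9.6 derives AUC to the last quantifiable time, AUC to infinity, half-life, Cmax and Tmax.
- SAP 10.7 limits the PK set to subjects with "sufficient concentration data to obtain reliable estimates of the key PK parameters".
- SAP 11.7 has its own rule for pre-dose values: "Baseline is defined as the latest non-missing measurement prior to IMP administration including repeat assessments and unscheduled visits".

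On the analyte, Protocol 4.3 states: "At normal levels of 200-300 mg/L, it is the fourth most abundant protein in the circulation". The same section says the drug is identical to the natural protein, and Protocol 11.4.3 says the PK specimens are measured for pGSN. Protocol 9.3 schedules two pre-dose samples, one before Dose #1 and a second one "For Dose #3: within 15 minutes predose".

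**The concern.** Setting a missing pre-dose value to 0 can be reasonable for a foreign compound before the first dose. Here the assay measures a protein that every subject already carries, so a lost or refused sample says nothing about its level, and 0 is wrong even in a depleted patient. It is most wrong before Dose #3 in the rhu-pGSN arm, where drug from two doses adds to the endogenous level. SAP 9.1 gives no reason for treating a missing pre-dose value differently from a missing post-dose one.

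The rule can also disagree with SAP 11.7. If the sample just before Dose #1 is missing but an earlier pretreatment sample exists, 11.7 uses the real value and 9.1 records 0.

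The parameter rule fails on dimensions. The LLOQ is a concentration, Tmax and half-life are times, and AUC is concentration multiplied by time. For Cmax the unit fits, but the fill is an extreme low value.

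PK is a secondary objective, and so is the relation of baseline pGSN to clinical outcome. If imputed values reached that second analysis, a missing sample would be read as complete depletion.

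**Working it through.** The plan states no figure that depends on these rules, so there is nothing to reproduce. The steps below show what the rules do. Missing counts, LLOQ, concentrations and the 8 h half-life are assumptions. The 30 per arm is from Protocol 7.1 (Part 1).

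**1. Drug left at the Dose #3 pre-dose sample (rhu-pGSN arm).** Doses are at 0, 12 and 36 h, so this sample comes 36 h after Dose #1 and 24 h after Dose #2. With half-life h, the fraction of one dose's increment still present is 0.5^(24/h) + 0.5^(36/h).

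| Half-life | Sum | Remaining |
|---|---|---|
| 17 h | 0.376 + 0.230 | 61% |
| 12 h | 0.250 + 0.125 | 38% |
| 8 h | 0.125 + 0.044 | 17% |

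Protocol 4.4.2 reports a median above 17 h in non-ICU pneumonia patients. The shorter values are included because the Protocol Synopsis says the protein is consumed faster in severe illness. The endogenous level comes on top. The rule records 0.

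**2. Pre-dose summary with 3 of 30 values set to 0.** Scale the true mean to 1 and take a true CV of 0.30, so the mean square is 1 + 0.09 = 1.09.

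- Reported mean: 27/30 = 0.90, a fall of 10% at any true level (250 mg/L becomes 225 mg/L).
- Reported CV: sqrt(0.9 × 1.09 − 0.90²)/0.90 = sqrt(0.171)/0.90 = 0.46.
- Geometric mean and geometric CV: log(0) is undefined, so a single zero is enough to make both uncomputable.

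**3. Half-life with 3 of 30 values filled with the LLOQ.** The other 27 are set at 17 h, and 27 × 17 = 459. Take one and the same assay limit, 1 mg/L = 1000 ng/mL.

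| LLOQ written as | Arithmetic mean | Geometric mean |
|---|---|---|
| 1 (mg/L) | (459 + 3)/30 = 15.4 h | 17^0.9 × 1^0.1 = 12.8 h |
| 1000 (ng/mL) | (459 + 3000)/30 = 115.3 h | 17^0.9 × 1000^0.1 = 25.6 h |
| left missing | 17 h | 17 h |

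The answer depends on the unit chosen for the assay limit. That is the practical sign that the rule is dimensionally invalid.

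**4. Effect of the zero rule on AUC.** Linear trapezoid at 0, 1, 2, 6 and 8 h, with 8 h interpolated between the 6 h and 12 h samples. Assumed endogenous level 50-250 mg/L, dose increment 150-300 mg/L, half-life 8 or 17 h. Replacing the pre-dose value C0 with 0 removes C0 × 1 h/2 from the area. AUC0-8 in the affected subject changes by −1.1% to −4.5% after Dose #1 and by −2.2% to −4.8% after Dose #3. Cmax and Tmax do not change. AUC0-8 is the endpoint named in Protocol 5.2.2 and SAP 7.2.3; the derivation list in SAP 12.9.6 does not include it.

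**The case against.** The strongest reply is that the rules will rarely apply. SAP 10.7 admits only subjects with enough data for reliable estimates, Protocol 6.1 requires the first-dose pGSN sample to be repeated if it is mistimed, and post-dose values are not imputed. All of this stands and limits the reach. It does not remove the problem. Subjects may refuse some or all PK samples and stay in the trial, and a subject with an adequate profile can still lack one estimable parameter. Half-life and AUC to infinity are the likely cases, because Dose #1 sampling ends at 12 h.

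The 115.3 h figure can be called staged: ng/mL is the only concentration unit the SAP names for PK output, and the mg/L in Protocol 4.3 is background. That is fair, and the figure is an illustration only. The dimensional error does not depend on it.

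The clash with SAP 11.7 is conditional. The Schedule of Assessments starts pGSN sampling on Day 1, so two different values arise only when an earlier pretreatment sample exists and the repeat was missed.

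Finally, the pre-dose sentence also covers results below the LLOQ. There, 0 is off by less than one LLOQ, so that half is tolerable and should not be swept away with the rest. A zero from that source would still break the geometric statistics, although it is unlikely for so abundant a protein.

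**Conclusion.** The concern holds. Followed as written, SAP 9.1 puts false values into the PK tables: 0 for an endogenous protein that was not measured, and a concentration in place of a time or an AUC.

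The damage is to the pre-dose concentration summaries and plots and to the PK parameter tables. It would extend to the baseline-pGSN analysis if that uses imputed values. The effect on AUC0-8 is small, about 1-5% in an affected subject. The illustrated sizes rest on 3 of 30 missing and on an assumed LLOQ and assumed concentrations; the defect in the rules rests on none of these. PK is descriptive (SAP 16.1), and the primary efficacy and safety results, sample size and alpha are unaffected. The text should be corrected, but the trial's main conclusions do not turn on it.

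**What to change.** In SAP 9.1:

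- Take missing results out of the pre-dose sentence, so that it covers only results below the LLOQ.
- Delete the sentence that fills missing PK parameters with the LLOQ.
- State that missing concentrations, pre-dose or post-dose, and PK parameters that cannot be estimated stay missing, and that n is reported with each summary.
- Say how a pre-dose result below the LLOQ, now set to 0, is handled in the geometric mean and geometric CV.
- Align the text with the PK-set rule in 10.7 and the baseline rule in 11.7.

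The cost is SAP wording only, with no new data or tables. Fewer subjects will contribute to some PK summaries, but that smaller number is the count actually observed.
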